### Treatment-Emergent AEs (TEAEs)

Treatment emergent AEs (TEAEs) will be defined and summarized in four different ways:

[1] TEAEs in Part A: will be defined as all AEs starting on or after the date of first study medication in Part A and up to 70 days after the last dose of study medication in Part A and before the date of the first study medication in Part B if any.

[2] TEAEs in Part B prior to flare: will be defined as all AEs starting on or after the date of first study medication in Part B and up to 70 days after the last dose of study medication in Part B. AEs occurring more than 70 days after the last dose in Part B will not be considered treatment emergent, regardless of whether this occurs during the SFU period, or after a treatment gap of more than 70 days. AEs which emerge post-flare will be excluded from any summary tables of TEAEs in Part B prior to flare.

[3] TEAEs in Part B in subjects experiencing a flare: Pre-flare TEAEs in Part B will be defined as any TEAEs in Part B with an onset date before the start date of escape therapy. Post-flare TEAEs in Part B will be defined as any TEAEs in Part B with an onset date on or after the start date of escape therapy.

[4] TEAEs in Part B under CZP full-dose therapy: These will be defined for subjects in the FDS who ever received a dose of CZP 200mg Q2W during Part B as double-blind or as escape treatment.

TEAEs in Part B under CZP full-dose therapy will be defined as follows:

- In subjects randomized into Part B to the PBO or CZP 200mg Q4W arm who do experience a flare and do escape to CZP full-dose therapy, TEAEs under CZP full-dose therapy will include all post-flare TEAEs in Part B
- In subjects randomized into Part B to CZP 200mg Q2W arm, TEAEs under CZP full-dose therapy will include all TEAEs in Part B

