(9) will be manually identified by the study physician from the previously described any serious TEAEs tables. No separate tables will be produced.

In addition, while not considered to be AEs of interest, following types of events will also be summarized:

- Hepatic events
- Hypersensitivity reactions and anaphylactic reactions

Hepatic events will be identified in the set of all TEAEs using following SMQs:

- Cholestasis and jaundice of hepatic origin (SMQ);
- Hepatic failure, fibrosis, and cirrhosis and other liver damage-related conditions (SMQ);
- Hepatitis, non-infectious (SMQ);
- Liver-related investigations, signs and symptoms (SMQ);
- Liver-related coagulation and bleeding disturbances (SMQ)

Hypersensitivity reactions and anaphylactic reactions will be summarized together.

Corresponding set of tables will include incidence of following types of events:

- Any hypersensitivity and anaphylactic reactions
- Any hypersensitivity reactions
- Any anaphylactic reactions

All TEAEs that emerge within one day of when a study medication injection reaction was received which code to the following PTs will be considered to be a hypersensitivity reaction and included in the summary tables:

- Administration site hypersensitivity
- Documented hypersensitivity to administered product
- Drug hypersensitivity
- Hypersensitivity
- Hypersensitivity vasculitis
- Infusion site hypersensitivity
- Injection site hypersensitivity
- Medical device site hypersensitivity
- Type II hypersensitivity
- Type IV hypersensitivity reaction

Injection reactions are identified by the investigator on the eCRF.

An algorithmic approach will be used to identify TEAEs that are considered to be anaphylactic reactions. PTs are separated into the 4 distinct categories (A, B, C, D) prior to the algorithmic approach being applied.

All TEAEs that emerge within one day of when a study medication injection reaction was received, and which fulfill any of the following 3 criteria will be included in the summary tables:

- If a subject reports any TEAE which codes to a PT included in Category A, then the event will be flagged as an anaphylactic reaction and summarized as such in the tables.

- If a subject reports any TEAE which codes to a PT included in Category B and reports any TEAE which codes to a PT included in Category C, and both TEAEs have the same start date, then both events will be flagged as anaphylactic reactions and summarized as such in the tables.

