This document contains information used to support any marketing authorization application and any extensions or variations thereof.  
REDACTED COPY

- Cardiac arrest
- Cardio-respiratory arrest
- Cardiovascular insufficiency
- Diastolic hypotension
- Hypotension

The following AE summary tables (for the Parts/Analysis sets a, b, c, d) will be used as the basis for presentation of AEs of interest as well as for hepatic events, hypersensitivity reactions and anaphylactic reactions:

- All TEAEs by primary SOC, HLT, and PT (applies to opportunistic infections [1], [2], hepatic events, hypersensitivity reactions and anaphylactic reactions)
- All serious TEAEs by primary SOC, HLT, and PT (applies to [3], [5], [6] and [7])

EAIR and EAER will be calculated and included in these summary tables of AEs of interest.

Finally, a summary of all TEAEs which emerged at any time during the study (Part A or Part B) while on CZP 200mg Q2W will be produced. This summary will include all subjects in the SS and all subjects in the SSB who received CZP 200mg Q2W during Part B (either as randomized treatment or as escape treatment). EAIR and EAER will be calculated and included in this summary table.

TEAEs which emerged at any time during the study while on CZP 200mg Q2W will be defined as follows:

- In subjects not randomized into Part B, TEAEs under CZP full-dose therapy will be defined as all AEs starting on or after the date of first CZP full-dose therapy in Part A and up to 70 days after the last dose of study medication in Part A.
- In subjects randomized into Part B to the PBO or CZP 200mg Q4W arm who do not experience a flare and do not escape to CZP full-dose therapy, TEAEs under CZP full-dose therapy will be defined as all AEs starting on or after the date of first study medication in Part A and up to 70 days after the last dose of study medication in Part A and before the date of the first study medication in Part B.
- In subjects randomized into Part B to the PBO or CZP 200mg Q4W arm who do experience a flare and do escape to CZP full-dose therapy, TEAEs under CZP full-dose therapy will include all post-flare TEAEs in Part B.
- In subjects randomized into Part B to CZP 200mg Q2W arm, TEAEs under CZP full-dose therapy will include all TEAEs in Part A and Part B.

AE data will be listed. A glossary for the AE listing will detail the verbatim terms that are coded to each SOC, HLT, and PT.

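### The hypersensitivity and anaphylaxis summary counts only events within one day of an investigator-identified injection reaction, so a coded reaction on a dosing day can be left out of it

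*SAP*

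**What the plan says.** SAP Section 10.2 (AE Summaries) plans one set of tables with three lines: hypersensitivity and anaphylactic reactions combined, hypersensitivity alone, and anaphylaxis alone.

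- **Hypersensitivity.** The rule takes "All TEAEs that emerge within one day of when a study medication injection reaction was received which code to the following PTs", followed by ten preferred terms (PTs). One of these is "Type IV hypersensitivity reaction".
- **Anaphylaxis.** PTs are sorted into Categories A to D. The algorithm is applied to "All TEAEs that emerge within one day of when a study medication injection reaction was received, and which fulfill any of the following 3 criteria". The first criterion is any Category A term; the other two are same-day combinations of Categories B, C and D.
- **Anchor.** Between the two rules the SAP states: "Injection reactions are identified by the investigator on the eCRF". The log for SAP Amendment 2 (Change #63) shows that this sentence was added at that amendment.
- **Output.** The table format is "All TEAEs by primary SOC, HLT, and PT (applies to opportunistic infections [1], [2], hepatic events, hypersensitivity reactions and anaphylactic reactions".

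The other event group handled alongside this one has no such condition: "Hepatic events will be identified in the set of all TEAEs using following SMQs".

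**The concern.** Both rules test how close an event is to an injection reaction, not to an injection. Because the SAP says that injection reactions are what the investigator identifies on the eCRF, the literal rule makes an investigator's entry a precondition for counting. An event coded to *Anaphylactic reaction* or *Anaphylactic shock* on a dosing day would be missing from the line headed anaphylactic reactions if no injection reaction had been identified.

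The four-category algorithm works from coded terms, so it could act as a check that does not depend on the investigator's label. With the condition in front of it, it can only work near events already labelled. The summary is planned for all four adverse event sets, including subjects who flared and started escape treatment. A reader of the finished table would have no sign that an investigator entry had been required.

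**Working it through.** The plan states no figure here, so the check is a reading of the rule against cases.

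**Two possible anchors.** Reading A takes the text literally: the anchor is the investigator-identified injection reaction. Reading B treats injection reaction as a slip for injection, so the anchor is the dosing date.

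| Event | Reading A | Reading B |
|---|---|---|
| *Anaphylactic reaction* on a dosing day, injection reaction identified that day | counted | counted |
| *Anaphylactic reaction* on a dosing day, no injection reaction identified | **not counted** | counted |
| Listed PT with onset more than one day from any injection, itself identified as an injection reaction | counted (within one day of itself) | **not counted** |
| Listed PT with onset more than one day from any injection, none identified | not counted | not counted |

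Row 2 is the problem under the literal text. Row 3 shows that late onset alone does not exclude an event under Reading A. The two kinds of loss therefore come from different anchors and cannot be added together.

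**Fallback.** Hepatic events are searched among all TEAEs. Opportunistic infections use a PT list plus manual physician review. Demyelination uses a narrow-scope MedDRA query over TEAEs. For hypersensitivity and anaphylaxis Section 10.2 gives no unrestricted search and no manual review, and Category A terms must pass the same condition.

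**Where an excluded event still appears.** It stays in the all-TEAE table by PT (sets a to d), the serious TEAE table if serious, the exposure-adjusted rate tables for both, and the AE listing. Only the dedicated summary and its rates depend on the condition.

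**Size under Reading A.** If the investigator identifies an injection reaction close to a share *p* of qualifying dosing-day events, the summary misses 1 − *p* of them. The document gives no basis for *p*.

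**Scale of the window under Reading B only.** Assume all Part A injections are on schedule.

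- Injections at Weeks 0, 2, …, 46 (Section 12.2): 24.
- Time at risk (Section 10.1.1), last minus first injection plus 70 days: 46 × 7 + 70 = 392 days. If censored at the first Part B dose at Week 48: 48 × 7 = 336 days.
- Injection day plus the next day: 24 × 2 = 48 days, so 48/392 = 12.2% or 48/336 = 14.3%.
- One day either side, leaving out the day before the first dose: 24 × 3 − 1 = 71 days, so 71/392 = 18.1% or 71/336 = 21.1%.

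An onset in the remaining 79% to 88% of Part A time at risk could not be counted. This is a share of calendar time, not of events. It says only that the one-day window is narrow beside a treatment-emergent period running "up to 70 days after the last dose of study medication in Part A".

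**The case against.** The strongest reply is that the phrase is a slip. One receives an injection, not a reaction, so the authors may have meant injection in both places. If so, the missing-entry problem disappears. This is possible but not settled by the text: the phrase occurs twice, and Amendment 2 added a sentence saying who identifies injection reactions instead of changing the term. A programmer working from the SAP would reasonably follow the literal version.

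A second reply is that limiting the summary to acute reactions is a legitimate choice. That stands as far as the one-day window goes. It does not justify the investigator condition, for which the SAP gives no reason.

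A third reply is that the eCRF is not shown, so nobody can tell how often a dosing-day anaphylactic event would lack an injection-reaction entry. That stands, and it is why no percentage is given.

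A reader might also infer more than the SAP supports:

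- *That these events vanish from safety reporting.* They do not; the general tables and the listings carry them.
- *That delayed reactions can never be counted.* That requires the injection date as anchor, which is the reading under which the missing-entry problem falls away.
- *That these are adverse events of interest under the SAP.* Section 10.2 expressly says they are not, while still committing to summarise them.

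**Conclusion.** The point holds as a definitional fault of moderate severity. As written, the rule can omit a coded anaphylactic or hypersensitivity reaction on a dosing day from the summary meant to report such reactions, and nothing in Section 10.2 recovers it there. Compared with an unrestricted search on the same terms, the count can be equal or lower but never higher. How much lower cannot be determined from the document.

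This conclusion assumes the literal reading. Under the alternative reading the rule captures row 2, but the text is then wrong at the step that defines the table and must still be corrected. Under either reading a one-day window can leave out later onsets of terms the SAP itself lists, such as *Type IV hypersensitivity reaction*. The summary is descriptive, with no hypothesis test and no bearing on the primary or secondary efficacy analyses, which is why the severity is not higher.

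**What to change.** 1. In both sentences, change the anchor from receipt of an injection reaction to administration of an injection. Injection dates are already needed for exposure (Section 10.1) and compliance (Section 12.2). Attach no investigator-identification condition.
2. Keep the one-day window around the injection date, in particular for the Category B, C and D combinations, whose terms are non-specific.
3. Add one row counting the ten listed hypersensitivity PTs and the Category A PTs among all TEAEs, whatever the time since injection. This shows later onsets. It also keeps listed and Category A events of the row 3 type, which the present wording admits and a dosing-date window alone would drop.

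The cost is two sentences of SAP text, a changed anchor date in the program and one extra table row, with no new data. The downside is that a few more non-specific events will appear in the summary.

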- The date of the last Part A full-dose CZP injection – date of first Part A full-dose CZP injection + 70 days for subjects not randomized into Part B. Patient time at risk will be censored at the date of earliest of the following events if any of these events occur prior to the completion of the 70-day period: final contact or death.
- The date of the last Part A full-dose CZP injection – date of first Part A full-dose CZP injection + 70 days for subjects randomized into Part B to the PBO or CZP 200mg Q4W arms who do not experience a flare and do not escape to CZP full-dose therapy. Patient time at risk will be censored at the date of earliest of the following events if any of these events occur prior to the completion of the 70-day period (first study medication administration in Part B, final contact or death).
- The sum of (date of the last Part A full-dose CZP injection – date of first Part A full-dose CZP injection + 70 days) [1] and (date of the last escape full-dose CZP injection – date of first escape full-dose CZP injection + 70 days) [2] for subjects randomized into Part B to the PBO or CZP 200mg Q4W arms who do experience a flare and do escape to CZP full-dose therapy. If first study medication administration in Part B occurs prior to the completion of the 70-day period for [1], [1] will be censored at the date of this event. If final contact or death occurs prior to the completion of the 70-day period for [2], [2] will be censored at the date of the earliest event.
- The date of the last Part B injection – date of first Part A full-dose CZP injection + 70 days for subjects randomized into Part B to CZP 200mg Q2W arm. If final contact or death occurs prior to the completion of the 70-day period, the patient time at risk will be censored at the date of the earliest event.

Total patient years at risk will be calculated as the sum of all the relevant patient time at risk (in days) divided by 365.25.

Exposure data will be listed.

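### The pooled full-dose CZP adverse-event table leaves out the Part A events of placebo and half-dose escapers, although the matching time-at-risk rule keeps their Part A time

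*SAP*

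**What the plan says.** The closing table of SAP Section 10.2 (AE Summaries) is to show "all TEAEs which emerged at any time during the study (Part A or Part B) while on CZP 200mg Q2W". It covers all subjects in the Safety Set and those in the Part B Safety Set who received full dose in Part B. On rates, the section says "EAIR and EAER will be calculated and included in this summary table".

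Four rules then say which events count:
- **Not randomized:** AEs from the first full dose in Part A to 70 days after the last Part A dose.
- **Placebo or Q4W, neither flare nor escape:** AEs from the first Part A dose to 70 days after the last one, and before the first Part B dose.
- **Placebo or Q4W, flare and escape:** for subjects "who do experience a flare and do escape to CZP full-dose therapy, TEAEs under CZP full-dose therapy will include all post-flare TEAEs in Part B".
- **Q2W arm:** "TEAEs under CZP full-dose therapy will include all TEAEs in Part A and Part B".

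Section 10.1.3 defines full-dose exposure and time at risk over Part A and Part B, in a single column on the Safety Set. For placebo and Q4W escapers, time at risk is "The sum of (date of the last Part A full-dose CZP injection" minus the first such injection, plus 70 days) and the corresponding escape segment. The Part A segment is censored at the first Part B dose.

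**The concern.** Every subject received the same open-label full-dose treatment in Part A. Three of the four rules count Part A events and the escaper rule does not, and no reason is given. The rule repeats the escaper definition used earlier in Section 10.2 for full-dose TEAEs in Part B only, where restricting to post-flare events is right. In a table spanning both parts it looks like a carry-over. The changes to Section 10.2 logged in Section 12.4 do not touch it, so it is current text.

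With the Section 10.1.3 denominator, escapers add Part A patient-years that cannot hold a counted event, so the error always lowers the rates. This is the only AE table that pools full-dose exposure from both parts. The omitted group is also selected by outcome, since its members flared.

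**Working it through.** The SAP states no figure for this table, so the check sizes the effect from the planning numbers.

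**Inputs from the SAP**
- Section 2.4: 750 enrolled, 28% randomized. 750 × 0.28 = 210, or 70 per arm, as stated; 540 are not randomized.
- Section 2.4: no-flare proportions of 75% (Q4W) and 45% (placebo).
- Section 12.2: last Part A dose at Week 46. Section 2.3.4: last Part B dose at Week 94.
- Section 10.1.3: 70 days added after the last dose; Part A time censored at the first Part B dose (Week 48, day 336) for placebo and Q4W subjects.

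**Assumptions not in the SAP**
- Every planned placebo or Q4W flare leads to escape.
- Escape dosing averages 24 weeks from first to last dose.
- Non-randomized subjects complete Part A dosing, and Q2W subjects dose to Week 94.
- One constant event rate applies throughout.

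**Escapers:** 70 × 0.55 + 70 × 0.25 = 38.5 + 17.5 = 56. The remaining 140 − 56 = 84 do not escape.

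**Patient-years (days ÷ 365.25)**

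| Class | Calculation | Patient-years |
|---|---|---|
| Not randomized | 540 × (322 + 70 = 392) | 579.5 |
| Placebo/Q4W, no escape | 84 × 336 | 77.3 |
| Escapers, Part A | 56 × 336 | 51.5 |
| Escapers, escape | 56 × (168 + 70 = 238) | 36.5 |
| Q2W arm | 70 × (658 + 70 = 728) | 139.5 |
| Total | | 884.3 |

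**EAER.** With a constant rate, reported ÷ true = 1 − (escapers' Part A time ÷ total) = 1 − 51.5/884.3 = 0.942, or about 5.8% too low. Counting the Part A events restores 1.00. Among escapers alone, 51.5/(51.5 + 36.5) = 59% of time at risk has no countable event (69% with 12 weeks of escape dosing, 49% with 40).

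**Range**
- 28 escapers: 25.8/866.1 = 3.0%.
- 77 escapers (55% of all 140): 70.8/898.0 = 7.9%.
- 56 escapers, non-randomized subjects with half the Part A dosing time: 51.5/646.3 = 8.0%.
- Both of the last two: the non-randomized class becomes 540 × (161 + 70)/365.25 = 341.5, the total becomes 898.0 − 579.5 + 341.5 = 660.0, and 70.8/660.0 = 10.7%.

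**EAIR and percentages.** An escaper whose only event fell in Part A counts as event-free, keeps full time at risk in the EAIR denominator, and stays in the Safety Set denominator of the crude percentage. Both measures move down. The size depends on the event, so no single factor applies.

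**The case against.** - **The verb include need not be exhaustive, and the scope sentence shows the intent.** The intent is clear, so this is an internal inconsistency and not a chosen method. But the Q2W rule uses the same verb and names both parts, so a programmer following the text would leave Part A out for escapers.
- **Section 10.2 does not cite Section 10.1.3.** Correct: the denominator mismatch is an inference. Section 10.2 says only that rates use patient-years at risk. No other rule covers full dose across both parts, and the conflict with the table's scope stands without it.
- **No event goes unreported.** Correct. Escapers' Part A TEAEs, serious ones included, appear in the Part A tables on the Safety Set with their own rates, and all AEs are listed. A reader might infer that safety events are hidden; the loss is confined to the pooled table.
- **Subjects who withdraw in Part B without escaping.** A reader might infer that they fit no rule and lose their Part A events too, because Section 3.2.22 counts withdrawal as flare. The SAP does not establish this. Section 4.2 ties that convention to the efficacy imputation. Section 10.2 splits pre- and post-flare at the start of escape therapy and bases its flare tables on the Escape Therapy Set. Section 3.6.9 defines the Flared Set by IXRS criteria and entry to the Escape Part, and withdrawal is not among them. On that reading these subjects fall under the second rule. What remains is ambiguity, plus the subject moved to escape by IXRS who never receives an escape dose, a case Section 5.1 allows for.

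**Conclusion.** The inconsistency is real. For placebo and Q4W escapers the pooled table counts only post-flare events, against its own scope and against the only time-at-risk rule that fits it. In the planning case the pooled EAER is about 6% too low, with a range of about 3% to 11%. The central figure rests on 56 escapers, 24 weeks of escape dosing, full Part A completion by non-randomized subjects and a constant event rate. The 56 is an upper figure at the planned flare rates, because flares imputed from withdrawal do not lead to escape. EAIR and crude percentages are lowered as well.

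This should be fixed but is not critical. It concerns one descriptive single-column safety table with no comparison between arms, its missing events are reported elsewhere, and the primary analysis is untouched.

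**What to change.** 1. In the closing table of Section 10.2, define the events for placebo and Q4W escapers as Part A TEAEs (from the first Part A dose, up to 70 days after the last Part A dose and before the first Part B dose) plus all post-flare TEAEs in Part B.
2. Cite Section 10.1.3 there as the source of the patient-years at risk.
3. In the rule for placebo and Q4W subjects who neither flare nor escape, and in its counterparts in Section 10.1.3, make the condition simply that they do not escape. Subjects counted as flared who never receive an escape dose then have a defined place.

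The cost is a few lines of SAP wording and one derivation change. Reported rates in this table would rise slightly; no other table changes because of items 1 and 2, and item 3 only removes ambiguity in the full-dose exposure summary.
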